Specifically, DJ stent-related symptoms are urinary frequency (50–60%), sexual dysfunction (male, 42–82% and female, 30–86%), reduced work capacity (58%), urgency (57–60%), dysuria (40%), flank pain (19–32%), incomplete emptying (76%), suprapubic pain (30%), hematuria (25%), and reduced quality of life (QOL) in approximately 80% of the patients[4]. It is reported that an important factor of stent-related symptoms is the pressure transmitted to the renal pelvis during voiding and trigonal irritation by the intravesicular part of the stent[5]. For this reason, several attempts to minimize stent-related symptoms have recently been reported. Pharmacologic management is one such trial[6]. Symptoms of stent discomfort, including bladder irritation symptoms and flank pain or discomfort, are

generally treated with oral analgesics, such as narcotics and anti-inflammatory medications; however these medications are only moderately effective.

Alpha-blockers alleviate bladder irritation due to stents, resulting in reduced incidence of dysuria, frequency, and pain compared to placebo[7]. Additionally, solifenacina anticholinergic has also showed significant benefits in lower urinary tract symptoms, stent-related pain and hematuria[8].

RATIONALE:

A comparison between taking either an alpha-blocker (tamsulosin) or an anti-cholinergic (solifenacina) to alleviate ureteral stent-related symptoms after patients have undergone Dj stenting prior to Extracorporeal shockwave lithotripsy (ESWL), Ureteroscopy (URS) with DJ stent placement or Percutaneous nephrolithotomy (PCNL) with DJ stent placement has not yet been done in Pakistan.

OBJECTIVE:

In this study, we will assess the comparison between an alpha-blocker (tamsulosin) and an anti-cholinergic (solifenacina) in the treatment of ureteral stent-related symptoms using the Ureteral Stent Symptom Questionnaire (USSQ).

OPERATIONAL DEFINITIONS:

Extra corporeal shockwave lithotripsy: A procedure that utilizes shockwaves to fragment kidney stones that can then pass through the urinary tract and be removed.

DJ Stent: A double-J stent is a ureteral stent with curving ends that prevent the stent slipping into the bladder or the kidney and allows continuous drainage of urine into the bladder.

Lower Urinary Tract Symptoms: Lower urinary tract symptoms (LUTS) include voiding or storage symptoms such as:-

Hesitancy; Difficulty starting or maintaining a urine stream

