Poor and intermittent stream; Intermittent urination is usually a sign of significant underlying bladder problem, most often incomplete bladder emptying can predispose to urinary tract infections, bladder stone formation, and renal insufficiency (damage to the kidneys).

Incomplete bladder emptying; Incomplete bladder emptying occurs when the muscles of the bladder are not able to squeeze properly to empty the bladder.

Frequency; Its normal and how many times is too frequent to urinate.

Urgency; Urinary urgency occurs when the pressure in the bladder builds suddenly, and it becomes difficult to hold in the urine.

Nocturia; the need for patients to get up at night on a regular basis to urinate

Alpha Blockers: Alpha blockers are also known as α -blockers or α -adrenoreceptor antagonists, are a class of pharmacological agents that act as antagonists on α -adrenergic receptors.

Anticholinergic: Anticholinergic drugs block the action of a neurotransmitter called acetylcholine. This inhibits nerve impulses responsible for involuntary muscle movements and various bodily functions. These drugs can treat a variety of conditions, from overactive bladder to chronic obstructive pulmonary disorder.

USSQ: Ureteral Stent Symptoms Questionnaire; a psychometrically valid measure to evaluate symptoms and impact on quality of life of ureteral stents.

HYPOTHESIS:

Solifenacin group have better outcome in comparison to Tamsulosin.

MATERIAL AND METHODS:

Study Design: Comparative study

Setting: Study will be conducted Department of Urology, Liaquat National Hospital Karachi. It will include the patients who had have complaints voiding symptoms like increased urinary frequency, urgency dysuria, incomplete bladder emptying and supra pubic pain.

Study Duration: 6 months after approval of synopsis.

Sampling Technique: non-probability consecutive sampling.

Sample size: The sample size is calculated by using the mean \pm SD of USSQ score i.e. 76 \pm 8 in tamsulosin group and 61 \pm 8.8 in solefinacin group. Open Epi Software is used for sample size calculation by taking power of test = 90% and confidence interval 95%, the total calculated sample is 14 patients (7 in each group). To improve the power the study, we will have 30 patients in each group.

Sample selection:

Inclusion criteria:

- Between the ages of 20 and 50 years,

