Patient's data will be compiled and analyzed through statistical package for Social Sciences (SPSS) Version 25. Normality of the data will be checked by Shapiro wilk's test. Mean \pm SD will be calculated for quantitative variable for groups i.e. age, height, weight, body mass index, length of stent placed and total USSQ score. If the data is non normal, median (iqr) will be reported instead of mean \pm SD. Frequency and percentage will be computed for qualitative variables for groups like gender, any addiction, diabetes, hypertension, smoker, occupation, surgical procedure and indications of stent placement. ANOVA will be applied to see the mean differences between groups. Chi square test or Fischer exact test will be used for finding association between categorical variables. Post stratification will be done on age, gender, height, weight, body mass index, any addiction, diabetes, hypertension, smoker, occupation, surgical procedure and indications of stent placement to see the effect of these modifiers on outcome. P-value ≤ 0.05 will be considered as significant.

ETHICAL CONSIDERATION:

Conducting a randomized control trial (RCT) comparing alpha-blocker and anti-cholinergic drugs involves several ethical considerations. It's crucial to prioritize the well-being and rights of participants while ensuring scientific rigor. Here are some ethical concerns associated with this a trial:

1. Informed Consent:

Ensuring that participants fully understand the nature of the study, potential risks, benefits, and alternatives before providing informed consent. It will be clearly communicated that participation is voluntary, and individuals have the right to withdraw at any time without facing negative consequences.

2. Participant Selection and Equity:

Ensuring that the selection criteria for participants are fair and do not disproportionately exclude certain demographic groups, potentially leading to biased results.

3. Confidentiality and Privacy:

Safeguarding participant confidentiality and privacy by implementing robust data protection measures. Clearly communicating how participant data will be handled, stored, and shared to maintain trust and comply with relevant privacy regulations.

4. Publication and Reporting:

Committing to transparent and timely reporting of study results, whether positive or negative, to contribute to scientific knowledge and prevent publication bias.

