10. Mirani K K, Ather M H (August 08, 2022) Translation and Validation of the Ureteral Stent Symptoms Questionnaire in Urdu. *Cureus* 14(8): e27764. DOI 10.7759/cureus.27764

ANNEXURE-I PROFORMA

GROUP: _____

Serial No: _____

Case No: _____

Patient's Name: _____

Patient's contact #: _____

S/O, D/O, W/O: _____

Patient's Age: _____ years

Gender: Male Female

Height: _____

Weight: _____

BMI: _____

Any Addiction: Yes No _____

Diabetes: Yes No

Hypertension: Yes No

Smoker: Yes No

Occupation: _____

Surgical Procedure: _____

Indication of stent placement: _____

Date of stent placement: _____

Length of stent placed: _____ (cm)

Total USSQ score: _____

ANNEXURE-II USSQ(Stent in situ)

We are interested to know about various aspects of your health, following insertion of the stent and the effect the stent has had on your health.

**Please complete the following questionnaire, which has different sections.
Please answer all questions in each section.**

(We would be grateful if you could complete and post the questionnaire within seven days)

Please complete:

Today's Date: / /

Date of Birth: / /

You will see that some questions ask if you have a symptom occasionally, sometimes or most of the time.

Occasionally	=	less than one third of the time
Sometimes	=	between one and two thirds of the time
Most of the time	=	more than two thirds of the time

URINARY SYMPTOMS

Please answer the questions thinking about the urinary symptoms you have experienced following insertion of the stent.

Please put a tick in one box for each question

Please think about your experience since insertion of the stent.

U1. During the day, how often do you pass urine, on average?

Less than hourly	 5	Every 3 hourly	 2
Hourly	 4	Every 4 hours or more	 1
Every 2 hourly	 3		

U2. During the night, how many times do you have to get up to pass urine, on average?

None	 1	3	 4
1	 2	4 or more	 5
2	 3		

U3. Do you have to rush to the toilet to urinate?

Never	 1	Most of the time	 4

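### Stent length is collected and fixed before randomisation but only described; a pre-specified covariate-adjusted comparison of total USSQ could add modest precision to a valid unadjusted ANOVA

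*Combined protocol and SAP*

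**What the plan says.** - **Mechanism.** The background names two contributors to stent symptoms: pressure transmitted to the renal pelvis during voiding, and "trigonal irritation by the intravesicular part of the stent".
- **Collection.** The proforma (Annexure-I) has the item "Length of stent placed", in cm, together with height and the indication for stenting. It has one line for total USSQ.
- **Timing.** The Data Collection Procedure randomises patients 1:1 by lottery on the day of surgery, after the stent is in place. No stratification is described.
- **Analysis.** The Data Analysis Procedure gives the mean and SD by group for "length of stent placed and total USSQ score", among other variables, and compares groups by ANOVA with no covariate named. It continues: "Post stratification will be done on age, gender, height, weight, body mass index", followed by seven further variables including occupation, surgical procedure and indication. Stent length is not among the twelve. The threshold is: "P-value ≤ 0.05 will be considered as significant".
- **Sample size.** The design assumes USSQ 76 ± 8 on tamsulosin and 61 ± 8.8 on solifenacin, "taking power of test = 90% and confidence interval 95"%. It concludes: "the total calculated sample is 14 patients (7 in each group"). Enrolment is then raised to 30 per group.

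**The concern.** Treatment cannot affect a variable fixed before allocation, so stent length is a legitimate covariate. If it predicts symptoms, leaving it out keeps explainable variance in the error term, and a chance imbalance between two arms of 30 carries partly into the USSQ difference.

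Two features make baseline covariates more useful here. No pre-stent USSQ is planned, so the covariate that would usually be strongest is unavailable. Allocation is not stratified, so chance imbalance can be dealt with only in the analysis.

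Post-stratification does not fill the gap. It is described as a look at effect modifiers one at a time and yields no single adjusted treatment estimate. Adding stent length as a thirteenth stratifier would not supply one either.

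At stake are the width of the confidence interval and its robustness to imbalance.

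**Working it through.** **Inputs from the documents.** SDs 8 and 8.8; planned difference 76 − 61 = 15; 90% power; 95% confidence, taken as two-sided because sidedness is not stated; 30 per arm, so N = 60.

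**Assumed inputs.** R² is the share of within-arm USSQ variance that the covariates explain, and ρ is the correlation of stent length with USSQ. The documents give neither, so ranges are shown.

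**1. The plan's own figure.** Pooled SD = √((8² + 8.8²)/2) = 8.41. n per arm = 2 × (8.41 × (1.960 + 1.282)/15)² = 6.61, rounded up to 7. The stated 7 per group is reproduced.

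**2. Unadjusted comparison at 30 per arm.** SE = 8.41 × √(2/30) = 2.17. CI half-width = 2.002 × 2.171 = 4.35 points (t on 58 df). The difference detectable with 90% power is 7.16 points (noncentral t). Power at 15 points exceeds 99.9%.

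**3. Adjusted comparison with three covariates** (stent length, height, two-level indication). The expected variance is multiplied by (1 − R²) × (1 + 3/54), where 54 = N − 3 − 3. Residual df are 55, with t = 2.004. The CI ratio is √[(1 − R²) × 1.0556] × 2.004/2.002. Equivalent n is 30 divided by the squared ratio.

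| R² (assumed) | CI ratio | Half-width | Equivalent n per arm | Detectable at 90% power |
|---|---|---|---|---|
| 0 | 1.029 | 4.47 | 28.4 | 7.4 |
| 0.055 | 1.000 | 4.35 | 30.0 | 7.2 |
| 0.10 | 0.976 | 4.24 | 31.5 | 7.0 |
| 0.30 | 0.861 | 3.74 | 40.5 | 6.2 |

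**4. Stent length alone.** With one covariate the variance factor is 1 + 1/56 on 57 df. The half-width is 4.39 at ρ = 0, 4.18 at ρ = 0.3 and 3.80 at ρ = 0.5. Break-even is near ρ = 0.13.

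**5. Chance imbalance.** The SE of the between-arm difference in mean stent length is √(2/30) = 0.258 SD. A difference above 0.25 SD therefore occurs in about 33% of trials and one above 0.5 SD in about 5%. An imbalance of 0.5 SD moves the unadjusted USSQ difference by 0.5 × ρ × 8.41:

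- ρ = 0.1: 0.4 points
- ρ = 0.3: 1.3 points
- ρ = 0.5: 2.1 points

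**The case against.** The strongest case against is that this is a preference. Several parts of it stand.

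- **The planned test is valid.** Random imbalance is already reflected in the unadjusted standard error, and power at 15 points leaves nothing to gain in detecting the planned effect.
- **The link to mechanism is an inference.** The protocol names the part of the stent in the bladder, not total length. If length is chosen to fit the patient, it need not track that segment, and the documents do not say how it is chosen. Total USSQ also covers pain, general health, work and sexual matters, so a high R² cannot be taken for granted.
- **The plan is not blind to these variables.** Stent length is tabulated by group, so an imbalance would be visible. Height and indication are in the post-stratification list. The wider gap is that no covariate at all enters the outcome comparison.

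A reader might infer more than the documents support:

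- *That the precision is free.* Below R² of about 5.5% the interval gets wider.
- *That stent length is recorded before randomisation.* The text shows only that the stent is placed first. When the proforma is completed is not stated.
- *That an imbalance passes in full into the USSQ difference.* It is scaled by ρ.

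The objection does not remove the case for adjustment. The possible loss is limited to about 3% of CI width, and a pre-specified model settles covariate choice before results are seen, which the present text leaves open.

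**Conclusion.** The point holds as a minor improvement. Stent length is collected, is fixed before allocation, and is used only descriptively, while the outcome ANOVA adjusts for nothing. With three covariates and 30 per arm, the effect on the CI runs from about 3% wider (R² = 0) to about 14% narrower (R² = 0.30). The detectable difference falls from 7.2 to about 7.0 points at R² = 0.10 and 6.2 at R² = 0.30. The gain would matter mainly if the true difference is nearer 6 to 7 points than 15.

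These figures rest on an assumed R², a pooled SD of 8.41, two-sided testing and all 60 patients contributing a score. The documents do not show that the unadjusted analysis is wrong, or that any conclusion at the planned effect is at risk.

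**What to change.** Before any outcome data are seen, specify the primary comparison as a linear model (ANCOVA, available in SPSS) of total USSQ on treatment arm. Adjust for stent length and height, both continuous, and for indication for stenting, coded to two levels in advance. The inclusion criteria already describe two: relief of obstruction by ureteric calculi, and stenting after ureteroscopic lithotripsy. Height belongs with stent length because length relative to the patient is the better candidate proxy. Report the adjusted mean difference with its 95% CI, and give the unadjusted ANOVA as a supporting result. State also that stent length is taken from the placement record, so that its status as a pre-allocation value is documented.

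The cost is a sentence or two of analysis text, 3 of 58 residual degrees of freedom, and advance coding of indication, which is an open text field on the proforma. No new data and no more patients are needed.

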- Patients who consented for unilateral DJ stent placement to relieve upper urinary tract obstruction caused by ureteric calculi or after ureteroscopic lithotripsy for ureteral calculi

Exclusion criteria:

- Having a history of LUTS before DJ stent placement
- Patients with bilateral DJ stent placement.
- Produced Stent related complications (displacement of stent)

DATA COLLECTION PROCEDURE:

Patients fulfilling the inclusion criteria presenting via outpatient clinic or emergency department at Liaquat National hospital, will be included in the study after taking informed and written consent. The study will start after the approval of synopsis by CPSP and Ethical and Review board of Liaquat National Hospital.

Patients will be randomly allocated into two groups according to lottery method. The randomization process will be performed using random allocation and patients divided in ratio 1:1. Patients will be randomly assigned to one of the two study groups; group one (tamsulosin), and group two (solifenacin)

on the day of the surgery after placement of the stent. Patients in group 1 will receive tamsulosin capsule (Brand: Cap Tamsolin) 0.4 mg/day, while patients in group 2 will receive solifenacin tablet (Brand: Tab Solifen) 5 mg/day. The cost will be borne by the patient as these medications are routinely given to the patient post DJ stenting, irrespective of their participation in the study. The medication will be taken until removal of the stent. Patients will be reviewed 2 weeks after stenting in opd. The USSQ is the only validated scoring system for evaluation of ureteral stent-related symptoms [9] and therefore has to be used for comparing different treatments for alleviation of these symptoms. USSQ translated into Urdu will be used for patients who are unable to answer questionnaire in English [10].

DATA ANALYSIS PROCEDURE:

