Pleased  2	Unhappy  6
Mostly satisfied  3	Terrible  7
Mixed feelings (about equally satisfied and dissatisfied)  4	

Please go to next section --

BODY PAIN (for women):

This section asks about the **body pain or discomfort**, which you associate with the stent.

Please think about your experience **following insertion of the stent**.

P1. Do you experience body pain or discomfort in association with the stent?

[figure not shown]
YES ₁, please go to question P2

NO ₂, please go to next section on General Health

[figure not shown]
(Ignore questions P2 to P9)

P2. Think of the drawings below as the drawings of your body. Please **mark (X) or shade the site(s) where you experience pain or discomfort in association with the stent typically (e.g. during the day to day activities, whenever you pass urine)**

If you get pain at more than one site, please use a **separate mark for each site**.

Front View

[figure not shown]
Back View

The numbers I - IV represent following areas for the right and left sides

I – Kidney front/side area III – Bladder area II - Groin area IV – Kidney back (loin) area

Please use O for any other marked area and write the name of the site

P3. Please place a **mark (X)** to a point on the line below that indicates your pain or discomfort in association with the stent. **Please put a separate mark for each site** if the pain or discomfort is different in severity and write the corresponding number of each site used in the drawing above.

No Pain or discomfort

Worst Possible Pain

BODY PAIN (for men):

This section asks about the **body pain or discomfort, which you associate with the stent.**

Please think about your experience **following insertion of the stent.**

[figure not shown]
[figure not shown]
P1. Do you experience body pain or discomfort in association with the stent?

YES **1, please go to question P2**

NO **2, please go to next section on General Health** (Ignore questions P2 to P9)

P2. Thinking the drawings below as the drawings of your body, **mark (X) or shade the site(s) where you experience pain or discomfort in association with the stent typically (e.g. during the day to day activities, whenever you pass urine)**

If you get pain at more than one site, please use a **separate mark for each site.**

The numbers I - V represent following areas for the right and left side.

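### The main ANOVA of total USSQ names no sex term and post-stratification yields no sex-adjusted drug difference: a missed gain in precision, not a validity flaw

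*Combined protocol and SAP*

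**What the plan says.** - **Analysis.** The Data Analysis Procedure gives the comparison of means as "ANOVA will be applied to see the mean differences between groups". No covariate is named. The same section reports gender by group and lists it among twelve variables for post-stratification. The stated purpose is to look at how these modifiers affect the outcome; no combined, adjusted drug difference is defined.
- **Allocation.** The Data Collection Procedure states "Patients will be randomly allocated into two groups according to lottery method", in a 1:1 ratio. No stratification is described.
- **Data recorded.** The proforma (Annexure I) has a field for gender and one field for the total USSQ score.
- **Instrument.** Annexure II has separate body-pain pages. The women's page says "The numbers I - IV represent following areas for the right and left sides"; the men's page says "The numbers I - V represent following areas for the right and left side", area V being the penis. Both pages let the patient mark any other site with the letter O. Both ask, at P3, for separate severity marks where severity differs between sites. No rule says how those marks enter the total.
- **Size.** The sample-size paragraph plans on a mean of 76 with SD 8 "in tamsulosin group and 61 \pm 8.8 in solefinacin group", concludes that "the total calculated sample is 14 patients (7 in each group" are needed, and then says "we will have 30 patients in each group".

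**The concern.** Sex is fixed before allocation, is already collected, and is a variable the sponsor itself suspects of affecting the score. The pain section is also presented differently to men and women. If men and women differ in mean total USSQ, an ANOVA on treatment alone leaves that difference in the error term. In the one allocation the trial actually draws, any imbalance in sex then carries over into the estimated drug difference.

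Reporting gender by group would reveal an imbalance but not correct for it. Separate results for men and women do not supply the single estimate on which the hypothesis rests. If adjustment is chosen only after an imbalance is seen, it is a post hoc decision. What is at stake is precision and a prespecified answer to an imbalance.

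**Working it through.** **Inputs from the plan.** Means 76 and 61; SDs 8 and 8.8; "taking power of test = 90% and confidence interval 95"%, taken as two-sided alpha 0.05 because sidedness is not stated; 30 per arm.

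**Assumptions, because the plan gives no figure.** Share of men 50-70%. Difference in mean total USSQ between men and women (the sex gap) 4-8 points, with 0 to 10 covered by simulation. The SD of 8.41 below is treated as the total SD within an arm, since the planning SDs are for whole arms and not for one sex.

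**1. The plan's own figure.**
- Pooled SD = √((8² + 8.8²)/2) = √70.72 = 8.41.
- n per group = 2 × (8.41 × (1.960 + 1.282)/15)² = 6.61, rounded up to 7, so 14 in total. This reproduces the plan.
- By the normal approximation, power for 15 points is 91.6% at 7 per group and above 99.99% at 30 per group.
- Standard error (SE) of the drug difference at 30 per arm = 8.41 × √(2/30) = 2.17.

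**2. Chance imbalance in sex.** The SD of the difference in the share of men is √(2p(1−p)/30): 12.9 percentage points at p = 50% and 11.8 at 70%. By the exact binomial, a difference of at least 20 points (6 of 30) occurs in 15.5%, 14.7% and 12.0% of trials at 50%, 60% and 70% men.

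**3. Effect on one trial's estimate.** Shift = difference in share × sex gap: 0.20 × 4 = 0.8 points and 0.20 × 8 = 1.6 points. Relative to the SE, these are 0.8/2.17 = 0.37 and 1.6/2.17 = 0.74. Relative to the planned 15 points, they are 5% and 11%.

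**4. Difference detectable with 90% power.** Without a sex term it is 7.16 points (t distribution; the normal approximation gives 7.04). A sex term removes p(1−p) × gap² from the variance, so the figure scales with the remaining SD:

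| Sex gap | Men | Remaining SD | Detectable difference |
|---|---|---|---|
| 4 | 50% | √(70.72 − 4.00) = 8.17 | 7.16 × 8.17/8.41 = 6.96 |
| 4 | 70% | √(70.72 − 3.36) = 8.21 | 7.16 × 8.21/8.41 = 6.99 |
| 8 | 50% | √(70.72 − 16.00) = 7.40 | 7.16 × 7.40/8.41 = 6.30 |
| 8 | 70% | √(70.72 − 13.44) = 7.57 | 7.16 × 7.57/8.41 = 6.44 |

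The table takes the sexes as evenly split between the arms. Chance imbalance adds about 1% to the adjusted SE: with no sex gap it is 2.19-2.20, against 2.17 unadjusted.

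**5. Simulation** (40,000 trials per scenario, 30 per arm, total SD held at 8.41, 50% and 70% men, gaps 0 to 10).
- Average bias of the unadjusted difference: at most 0.02 points.
- Type I error: 0.048-0.052 without the sex term, 0.049-0.051 with it.
- Power for 15 points: about 100% either way.
- Power for 5 points: about 62% without the term; with it, 61-79% (50% men) or 61-76% (70% men) as the gap goes from 0 to 10.
- Reduction in SE from the sex term: none at a gap of 2, about 3-4% at 5, about 15-19% at 10.

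**The case against.** The strongest reply is that the trial is randomized, so chance imbalance in sex is random error that the ANOVA standard error already covers. That stands. A reader might infer from the different pain pages and the unstratified lottery that the drug comparison is biased or its p-value unreliable; the simulation shows neither.

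A reader might also infer that the fifth area makes men score higher. The documents do not support that. Women can mark further sites with the letter O, items P4 to P9 are printed once for both sexes, and no rule says whether P3 marks are summed, averaged or left out of the total. The missing scoring rule is a separate gap, which a sex term does not fill. The sex gap could be zero.

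A third reply is that other branches of the questionnaire also change which items are answered: no pain at P1, paid work, an active sex life. But those are answers given after stenting, and some are part of the outcome itself. Sex is fixed beforehand, so it is a legitimate covariate.

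Finally, the plan does not ignore sex: it records it, reports it by group and looks within strata. That is true, but the strata are small (at 70% men, about 21 men and 9 women per arm), and the plan still defines no adjusted overall difference.

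**Conclusion.** The point holds as an inexpensive improvement. The plan collects a baseline variable that it suspects of influencing the outcome, but does not use it in the comparison that decides the hypothesis. If the true difference is near 15 points, the conclusion will be the same either way. If it is nearer 5 points and the sexes differ substantially, a sex term gives a useful gain in power. It also guards against a shift of 0.8-1.6 points in the 12-16% of trials with an imbalance of 20 percentage points or more. If the sexes do not differ, almost nothing is gained or lost. All these sizes rest on the assumed share of men, the assumed sex gap, and 8.41 as the total SD.

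**What to change.** Before any outcome is examined, replace the ANOVA sentence, for total USSQ, with a linear model (two-factor ANOVA) containing treatment group and sex. Report the sex-adjusted drug difference with its 95% confidence interval as the primary result. Keep the gender-stratified results and label them exploratory.

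The cost is one or two sentences in the Data Analysis Procedure and one degree of freedom. It needs no new data, and the SPSS package already named can fit the model. Separate lottery slips for men and women are not needed: the model adjusts for imbalance. With consecutive enrolment and an unknown sex mix, two sets of slips could not be sized in advance to guarantee 30 per arm.

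### Post-stratifying 60 patients on 12 variables at p ≤ 0.05, with no interaction term and no exploratory label, would give unreliable modifier findings; the overall drug comparison is not affected

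*Combined protocol and SAP*

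**What the plan says.** The Data Analysis Procedure of the combined protocol and SAP names one test for means: "ANOVA will be applied to see the mean differences between groups". It then states: "Post stratification will be done on age, gender, height, weight, body mass index, any addiction, diabetes, hypertension, smoker, occupation, surgical procedure". The sentence ends with the twelfth variable and the purpose: "indications of stent placement to see the effect of these modifiers on outcome". One threshold follows, p ≤ 0.05, with nothing to separate the main comparison from the modifier results.

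The section names no test for use after stratification. It gives no treatment-by-factor term, multiplicity rule or exploratory label. It sets no cut-points for age, height, weight or BMI. Occupation, procedure and indication have no listed categories, and the proforma (Annexure I) leaves them as blank lines.

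The Hypothesis section has a single statement: "Solifenacin group have better outcome in comparison to Tamsulosin". The Sample size section plans 30 patients in each group.

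**The concern.** The word *modifiers* points to effect modification: does the drug difference depend on age, gender, diabetes and so on? If the drug comparison is simply repeated inside each stratum, the p-value there answers another question, namely whether the drugs differ in that stratum. Two errors can follow.

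- If the drugs are equal, many stratum tests at 0.05 will produce some chance positives.
- If one drug is better by the same amount in everyone, a small stratum can miss what its larger partner detects. The pair then reads as benefit in one kind of patient and none in the other.

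The plan has no test that separates this second pattern from real modification. At stake are any statements about who benefits, not the answer to the main question.

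**Working it through.** **Inputs from the documents.** Sample size section: USSQ total 76 ± 8 (tamsulosin) and 61 ± 8.8 (solifenacin), 90% power, 95% confidence, 7 per group calculated and 30 per group planned. Data Analysis Procedure: 12 variables, p ≤ 0.05.

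**Assumptions.** Two levels per factor, the stratum splits, a common SD and two-sided tests. The documents give no prevalences or cut-points.

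**1. The plan's own figure.** Common SD = √((8² + 8.8²)/2) = 8.41. Per group: (8² + 8.8²)(1.960 + 1.282)²/15² = 6.6, rounded up to 7, or 14 in total. This agrees with the plan. At 30 per group, power for 15 points exceeds 99.9%.

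**2. Equal drugs, tests within strata.** Simulated trials of 60 patients, with a t-test (the two-group ANOVA) in each stratum that had at least 2 per arm, 6,000 trials per layout. At least one stratum reached p ≤ 0.05 in:

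- 47% (exact 50/50 splits);
- 48% (random 50/50);
- 50% and 49% (two uneven layouts, with prevalences of 0.2–0.5 and 0.15–0.5);
- 51% (the first uneven layout, with procedure at three levels).

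Treating 24 stratum tests as independent would give 1 − 0.95²⁴ = 71%. That is too high, because every factor re-divides the same 60 outcomes.

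**3. The same 15-point benefit in every patient.** Power within a stratum depends on its size:

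| Patients per arm | Power at 15 points |
|---|---|
| 15 | 99.7% |
| 10 | 96.5% |
| 6 | 79.5% |
| 4 | 56.1% |

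For one factor, P(one stratum significant, the other not) = p₁(1 − p₂) + p₂(1 − p₁). Split 15/15 per arm: 2 × 0.997 × 0.003 = 0.6%. Split 24/6: power is above 99.99% and 79.5%, so about 21%.

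Across all 12 factors, the simulated chance of at least one such discordant factor was:

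| Splits | Smallest stratum tested | Chance |
|---|---|---|
| Even | 2 per arm | 4–9% |
| Uneven (assumed) | 5 per arm | about 34–40% |
| Uneven (assumed) | 2 per arm | 53–80% |

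With strata down to 2 per arm, the mean number of discordant factors was about 0.1 of 12 with even splits and 1.0–1.8 with uneven splits.

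Fifteen points is a favourable case. At an assumed uniform 7.5 points, one evenly split factor is already discordant with probability 2 × 0.655 × 0.345 = 45%.

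**4. Prognostic reading.** Twelve unadjusted tests of factor against score: 1 − 0.95¹² = 46.0%. Simulation gave 44–46%, except 10% at 15 points when every factor was exactly balanced within both arms.

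**5. What an interaction test would do.** Twelve interaction tests at 0.05 also give 1 − 0.95¹² = 46.0% (43–49% simulated). Bonferroni at 0.05/12 = 0.0042 lowers this to 4.9%, but power for a 7.5-point interaction with an even split falls from 41% to 13%.

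**6. Precision.** Overall SE = 8.41 × √(2/30) = 2.17, 95% CI ± 4.3. Interaction SE for an even two-level split = 8.41 × √(2/15 + 2/15) = 4.34, 95% CI ± 8.7. At 15% prevalence, 8.41 × √(2/4.5 + 2/25.5) = 6.08, 95% CI ± 12.2.

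**The case against.** The text does not say that the drugs will be compared within strata, or that a stratum p-value will be read as modification. A two-way ANOVA with interaction is neither stated nor excluded, and the sentence could mean prognostic effects on the score. That stands: what is certain is that the analysis is not specified. It does not remove the point, because each of these readings, run 12 times at p ≤ 0.05, gives roughly an even chance of at least one false finding when there is nothing to find.

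The high discordance figures depend on assumed prevalences and on testing very small strata. That also stands. They fall by roughly half at the upper end when 5 per arm are required, and four of the factors are continuous, so their splits are the analyst's choice. The equal-drugs figure barely depends on the splits.

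An interaction test alone does not lower the false-positive count. This is correct, and the fix does not rely on it for that.

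A reader might infer that the 12 variables undermine the trial's main result. The documents do not support that. There is one hypothesis, it concerns the overall comparison, and no section makes the conclusion depend on a subgroup.

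**Conclusion.** The point holds as a defect in the secondary analysis. Twelve modifiers in 60 patients, judged by the same p ≤ 0.05 as the main comparison and without a model for modification, would yield findings that cannot be relied on. This should be changed, although it does not threaten the overall drug comparison.

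On the within-stratum reading, about half of trials would show a significant stratum with equal drugs. How often a uniform benefit would look selective is much less certain: it runs from 4% to 80% across the assumed layouts and minimum stratum sizes, and the documents cannot narrow it. Confidence is moderate, because the wording leaves open which analysis is intended and every split is assumed.

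**What to change.** Replace the post-stratification sentence with wording such as:

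> For a short list of factors named before analysis, total USSQ score will be modelled as treatment + factor + treatment × factor; the interaction estimate and its 95% CI will be reported as exploratory. P ≤ 0.05 applies only to the single overall treatment comparison, and no stratum or interaction result supports the conclusion.

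The investigators need to choose the list before any outcome is analysed and fix the levels of each categorical factor. Keep continuous factors continuous. Use BMI rather than height, weight and BMI together, since BMI is computed from the other two. If prognostic effects are what is meant, report treatment + factor estimates with 95% CIs under the same exploratory label.

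The interaction model answers the modifier question. The protection against false positives comes from the short list and the label.

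The cost is a change of wording and a linear model in the SPSS software already planned, with no extra patients or data. There will be fewer subgroup tables. The interaction CIs will be wide, about ± 8.7 points for an even two-level split, so a CI that includes zero will not rule out modification.
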